6.6 Analyses

6.6.1 Primary Analyses

The result for each test will be compared with the ASIS for that anatomic site and organism. For each diagnostic test, PPA and NPA will be estimated using 95% Score confidence intervals. Confidence intervals will be estimated using the Score method.³⁴

In the primary analysis, we will follow the FDA guidance document for incorporating indeterminate ASIS or test results for the test under consideration that are equivocal.³⁴ Indeterminate ASIS results will be counted against the results for the test under consideration, as described in Tables 4 and 5. Tables 4 and 5 will be presented in the analysis report, showing all combinations of Infected/Indeterminate/Not Infected with all outcomes from the test under consideration (Positive/Equivocal/Negative/No result or Invalid)

If the test under consideration has “no result” because the test was not run and no attempt was made to test the sample, it will be excluded from the primary analysis.

Table 4. Use of the ASIS in calculation of the positive and negative percent agreement for the Company 2 Assay (Company 2) and Company 3 Assay (CT only).

| | ASIS | | |
|--|----------|----------------|--------------|
| | Infected | Indeterminate* | Not infected |
| | | | |

| | | | | |
|---|-----------|-----------------------|---|-----------------------|
| Result of Test under Consideration** | Positive | A | D | G |
| | Equivocal | B | E | H |
| | Negative | C | F | I |
| | No result | Exclude from analysis | | |
| | PPA | $A / (A+B+C+F)$ | | |
| | NPA | | | $I / (G + H + I + D)$ |

*The middle, indeterminate column will be included in the analyses as “Infected” or “Not infected” as described in the sensitivity analyses below.

**Per the ASIS definition in Section 2.3

Comprehensive sensitivity analyses will be conducted considering multiple scenarios. These include:

- Classify indeterminate tests on the basis of symptom status. Include indeterminate tests as infected if the participant is symptomatic in that compartment. Include indeterminate tests as not infected in the participant is asymptomatic in that compartment.
- Include all indeterminate tests as infected.
 - $PPA = (A+D) / (A+B+C+D+E+F)$
 - $NPA = I / (G+H+I)$
- Include all indeterminate tests as not infected.
 - $PPA = A / (A+B+C)$
 - $NPA = (F+I) / (D+E+F+G+H+I)$
- Considering indeterminate and equivocal test results as “missing”, with the assumption of missing at random, and model the missing results.
- Additional sensitivity analyses, including the use of latent class models, will be explored. Details will be in the statistical analysis plan.

Table 5. Use of the ASIS in calculation of the positive and negative percent agreement for the Company 1 Assay (Company 1) and Company 3 Assay (NG only).

| | | ASIS | | |
|---|-----------------------|-----------------------|----------------|---------------|
| | | Infected | Indeterminate* | Not infected |
| Result of Test under Consideration** | Positive/Detected | A | C | E |
| | Negative/Not detected | B | D | F |
| | No result | Exclude from analysis | | |
| | PPA | $A / (A+B+D)$ | | |
| | NPA | | | $F / (C+E+F)$ |

*The middle, indeterminate column will be included in the analyses as “Infected” or “Not infected” as described in the sensitivity analyses below.

**Per the ASIS definition in Section 2.3

If the test under consideration has “no result” because the test was not run and no attempt was made to test the sample or because of invalid ASIS results it will be excluded from the primary analysis.

Comprehensive sensitivity analyses will be conducted. These include:

- Classify indeterminate tests on the basis of symptom status. Include indeterminate tests as Infected if the participant is symptomatic in that compartment. Include indeterminate tests as not infected in the participant is asymptomatic in that compartment.

- Include all indeterminate tests as infected
 - $PPA = (A+C) / (A+B+C+D)$
 - $NPA = F / (E+F)$
- Include all indeterminate tests as not infected
 - $PPA = A / (A+B)$
 - $NPA = (D+F) / (C+D+E+F)$
- Additional sensitivity analyses that consider indeterminate results as “missing” and utilize imputation strategies, and graphical techniques
- Additional sensitivity analyses, including the use of latent class models, will be explored. Details will be in the statistical analysis plan.

There are pros and cons to the manner in which indeterminates are handled and the resulting calculations of PPA and NPA. The primary definition is the most conservative but is biased downwards. If $PPA > 90\%$ under this scenario, then the conclusion of $PPA > 90\%$ is clear. The second and third sensitivity analyses count indeterminates (treat all as infected or not infected, respectively) but may not be conservative for calculations of PPA and NPA.

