2.3 Outcome Measures

The anatomic site infected status (ASIS) will be determined for each anatomic site (pharyngeal and rectal) and each organism (NG and CT), as shown below in Table 2.

Possible ASIS outcomes are:

- Infected
- Not infected
- Indeterminate
- Invalid, exclude from analysis

The anatomic site is considered to be infected if both of the reference test results are positive. The anatomic site is considered to be not infected when both reference test results are negative. If there is discordance between the reference tests, an additional NAAT will be done as a tiebreaker. In this case, agreement of 2/3 of the reference NAATs will determine the ASIS. If two tests are equivocal or one equivocal and one not run, the third test result will stand as the ASIS if positive or negative. If two tests are not run, the ASIS will be considered invalid and will be excluded from the analysis. All possible combinations are shown in Table 2. The tiebreaker test will be run by the lab if any NAAT is not concordant with the others and interpreted only in the case of discordant results between the two planned reference tests for each assay. [redacted].

To determine the ASIS, the test result for each respective site (pharyngeal or rectal) and each organism (NG or CT) for each NAAT platform will be used. Possible outcomes for each assay are:

- **Company 1 Assay (Company 1)¹:** Not detected, detected, invalid (sample processing control or sample adequacy control failed), error (probe check control failed), or no result (insufficient data was collected, e.g. test aborted). Initial invalid, error, or no result tests will be repeated. If the repeat test returns invalid, error, or no result, the final result will be considered an invalid and will be categorized as no result (NR) for the ASIS determination and statistical analyses below. If the repeat test returns not detected (negative) or detected (positive), this will be the result used for the ASIS determination and statistical analyses.

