- **Company 2 Assay (Company 2)²:** Negative, positive, equivocal (result between positive and negative), invalid (run status is FAIL or other technical failure), or error (sample was not tested due to an error detected by the instrument). Initial equivocal, invalid, and error test results will be repeated. If the repeat test result returns equivocal, the final test result will be considered an equivocal test result for the ASIS determination and statistical analyses below. If the repeat test result returns invalid or error, the final test result will be categorized as equivocal if the initial test was equivocal and as no result (NR) if the initial test was invalid or error for the ASIS determination and statistical analyses below. If the repeat test returns negative or positive, this will be the result considered for the ASIS determination and statistical analyses.
- **Company 3 Assay (Company 3)³:** For NG, possible results are positive (detected, with cycle number less than or equal to the assay cut-off), negative (no evidence of amplification or cycle number greater than the assay cut-off), and error. An equivocal interpretation does not apply. For CT, possible results are positive (detected, with cycle number less than or equal to the assay cut-off), negative (no evidence of amplification), equivocal (cycle number beyond the assay cut-off), and error. A sample with initial interpretation of error (both CT and NG) or equivocal (CT only) will be retested. If the repeat test returns negative or positive, this will be the result considered for the ASIS determination and statistical analyses. If the repeat

test result is equivocal (CT only), the final test result will be considered equivocal for the ASIS determination and statistical analyses below. If the repeat test result is error, the final test result will be categorized as no result (NR) for the ASIS determination and statistical analyses below if the initial test result was error and as equivocal if the initial test result was equivocal (CT only).

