5.4.2. Final Analysis Considerations

Note: All dataset derivation programs for this endpoint will undergo independent results verification in accordance with CBAR PROG.10033; validation requirements for analysis programs are stated below.

As noted previously, for all final analyses, data collected from eCRFs or data entered by the laboratories in the laboratory information management system (LIMS) will be used. Data from additional sources such as machine data or issue tracking logs may be reviewed for clarification, but will not be used for analysis.

The result for each diagnostic test will be compared with the ASIS for that anatomic site and organism. PPA and NPA will also be estimated for each diagnostic test with 95% confidence intervals. Confidence intervals will be estimated using the Score method.⁸ If the test under consideration has "no result" because the test was not run and no attempt was made to test the sample, the test result will be excluded from primary analysis. If the ASIS result is invalid, this result will be excluded from the primary analysis.

FDA guidance documents will be followed as part of the primary analysis to incorporate indeterminate ASIS or test results for the test under consideration that are equivocal.⁹ It is recognized that there are pros and cons to the manner in which indeterminates are handled and how these impact the resulting estimates of PPA and NPA. The primary analysis approach is the most conservative and is biased downwards. If PPA is >90% under this scenario, then the conclusion of PPA >90% is clear.

Sensitivity analyses will be conducted as appropriate to evaluate the impact of diagnostic accuracy for a range of scenarios addressing indeterminate ASIS results. This will include counting indeterminate ASIS results against the results for the test under consideration with all combinations of Infected/Indeterminate/Not Infected with all outcomes from the test under consideration (Positive/Equivocal/Negative/No result or Invalid) evaluated. These analyses may not be conservative for calculations of PPA and NPA.

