5.4.3. Primary Analyses

The following will be conducted for the three diagnostic tests.

Note: Analysis programs will require independent results verification per CBAR PROG.10033.

 Table: For each diagnostic assay (including the tiebreaker assay), frequency of observed test outcomes by anatomical site and organism combination. [See Table 8 described in Section 5.3.2; data source: LAB DATA]

⁸ FDA. Establishing the performance characteristics of in vivo diagnostics devices for Chlamydia trachomatis and/or Neisseria gonorrhoeae: screening and diagnostic testing. (2011).

⁹ FDA. Establishing the performance characteristics of in vivo diagnostics devices for Chlamydia trachomatis and/or Neisseria gonorrhoeae: screening and diagnostic testing. (2011).

- b. Table: Frequency (%) of re-tests by clinic and platform. This will be conducted for each test under consideration and be presented by anatomical site and organism combination. [Data source: LAB DATA; DEMOG]
- c. Table: Listing and frequency (%) of re-tests results by platform. This will be conducted for each test under consideration and be presented by anatomical site and organism combination. [Data source: LAB DATA]
- d. Table/Figure: Frequency of comparator NAAT result and tiebreaker result combinations to define ASIS. This will be conducted for each test under consideration and be presented by anatomical site and organism combination. There will be a total of three tables to reflect the three tests under consideration. [See **Table 9** previously described in in Section 5.3.2; data source: LAB DATA]
- e. Table/Figure: Number (%) of observed total test results, ASIS results, and prevalence (i.e., infection) rate. This will be conducted for each test under consideration and be presented by anatomical site and organism combination. [See **Table 10** previously described in Section 5.3.2; data source: LAB DATA]
- f. Table: Observed infection rate by clinic. This will be conducted for each test under consideration and be presented by anatomical site and organism combination. [Data source: LAB DATA; DEMOG]
- g. Tables:
 - Cross comparison of number (%) of results of test under consideration versus ASIS;
 - Estimates of PPA and NPA with 95% Score confidence intervals;
 - Due to differences in PPA and NPA calculations for NAAT platforms that do not have an [redacted] result when it is the test under consideration, analysis results will be estimated and presented separately based on this distinction as follows:

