 - Table 11 and Table 12: Company 2 Assay (Company 2) and Company 3 Assay (Company 3).
 - Table 13 and Table 14: Company 1 Assay (Company 1) and Company 3 Assay (Company 3).
- h. Figure: Plot of PPA and 95% confidence interval band versus proportion of indeterminate ASIS results assumed to be positive (range of 0 to 1); vice-versa for NPA plot.
- i. Table: Using Fischer's exact test, the association between test results and randomized swab order will be examined. Associations will be conducted by anatomical site and organism combination.

Table 11: Result of Test under Consideration versus ASIS: Company 2 Assay (Company 2) and Company 3 Assay (Company 3)

		ASIS			
		Infected	Indeterminate	Not infected	
	Positive	A	D	G	
Result of Test under Consideration	Equivocal	В	E	Н	
	Negative	С	F	I	
	No result	Exclude from analysis ¹			
¹ Note: If the test under consideration has "no result" because the test was not run and no attempt was made to test the sample, the					

test result will be excluded from primary analysis. If the ASIS result is invalid, this result will be excluded from the primary analysis.

Table 12: Calculation of the positive and negative percent agreement: Company 2 Assay (Company 2) and Company 3 Assay (Company 3)

Analysis Type	PPA	NPA		
Primary Analysis	A / (A+B+C +F)	l / (G+H+l + D)		
Sensitivity Analysis Scenarios				
Classify indeterminates ¹ using symptom status reported	A / (A+B+C+F)	I / (G+H+I+D)		
from [SIGNS AND SYMPTOMS]				
Include all indeterminate tests as infected.	(A+D) / (A+B+C+D+E+F)	l / (G+H+I)		
Include all indeterminate tests as not infected.	A / (A+B+C)	(I+F) / (D+E+F+G+H+I)		
Consider indeterminate and equivocal test results as "missing", with the assumption of missing at random, and model the missing results. ²	A / (A+C)	l / (G+l)		
Classify indeterminate tests on the basis of symptom status. Include indeterminate tests as Infected if the participant is symptomatic in that compartment; include indeterminate tests as not infected in the participant is asymptomatic in that compartment. Cells B, D, E, F and H will be assigned or weighted to cells A, C, G and I based on modeling of the missing results.				

Table 13: Result of Test under Consideration versus ASIS: Company 1 Assay (Company 1) and Company 3 Assay (Company 3)

		ASIS			
		Infected	Indeterminate	Not infected	
	Positive/Detected	A	С	E	
Result of Test under Consideration	Negative/Not detected	В	D	F	
	No result	Exclude from analysis ¹			

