Note: If the test under consideration has "no result" because the test was not run and no attempt was made to test the sample, the					

¹ Note: If the test under consideration has "no result" because the test was not run and no attempt was made to test the sample, the test result will be excluded from primary analysis. If the ASIS result is invalid, this result will be excluded from the primary analysis.

Table 14: Calculation of the positive and negative percent agreement: Company 1 Assay (Company 1) and for the Company 3 Assay (Company 3)

Analysis Type	PPA	NPA
Primary Analysis	A / (A+B +D)	F / (C+E +F)
Sensitivity Analysis Scenarios		
Classify indeterminates ¹ using symptom status reported from [SIGNS AND SYMPTOMS]	A / (A+B+D)	F / (C+E+F)
Include all indeterminate tests as infected.	(A+C) / (A+B+C+D)	F / (E+F)
Include all indeterminate tests as not infected.	A / (A+B)	(D+F) / (C+D+E+F)
Consider indeterminate and equivocal test results as "missing", with the assumption of missing at random, and model the missing results. ²	A / (A+B)	F / (E+F)

¹ Classify indeterminate tests on the basis of symptom status. Include indeterminate tests as Infected if the participant is symptomatic in that compartment; include indeterminate tests as not infected in the participant is asymptomatic in that compartment.
² Cells C and D will be assigned or weighted to cells A, B, E and F based on modeling of the missing results.

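### A test under consideration that was attempted but ends as no result is dropped from PPA and NPA, while the text ties exclusion to tests never attempted, and no planned formula counts these failures

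*Protocol*

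**What the plan says.** **How a failed test becomes NR.** Protocol 2.3 has an initial invalid or error result (for Company 1, also no result) repeated. For Company 1, if the repeat fails too, "the final result will be considered an invalid and will be categorized as no result (NR) for the ASIS determination and statistical analyses below". For Company 2, a repeat that is invalid or in error is classed "as no result (NR) if the initial test was invalid or error for the ASIS determination and statistical analyses below", and Company 3 has the same rule for error. SAP 5.1 adds that a missing expected repeat gives no result. In both documents an initial equivocal is treated differently: if its repeat fails (protocol 2.3) or is missing (SAP 5.1), the final result is equivocal.

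**What the tables do.** The No result row of protocol Tables 4 and 5 reads "Exclude from analysis", with no cell letter and no condition. SAP Tables 11 and 13 do the same.

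**What the text says.** Protocol 6.6.1 excludes a no result "because the test was not run and no attempt was made to test the sample, it will be excluded from the primary analysis". SAP section D repeats this, and SAP 5.4.2 says that when "the test was not run and no attempt was made to test the sample, the test result will be excluded from primary analysis". The footnotes on the No result row of SAP Tables 11 and 13 use the same condition: "because the test was not run and no attempt was made to test the sample, the test result will be excluded from primary analysis". The only other reason given, beside protocol Table 5, in SAP 5.4.2 and in those footnotes, is an invalid ASIS.

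**What NR means.** The abbreviation lists in both documents define it as no test run. The notes to protocol Table 2 and SAP Table 4 also include invalid results.

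**The concern.** A sample that was tested, failed, and then failed again or had no repeat result fits neither stated reason for exclusion: an attempt was made, and the ASIS may be perfectly valid. The row drops it all the same. The row and the sentence explaining it do not match, and the two NR definitions pull in different directions.

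The direction of the effect is fixed. Leaving such failures out can only make PPA and NPA equal to or higher than counting them as non-agreement. Protocol 6.6.1 and SAP 5.4.2 nevertheless call the primary definition the most conservative, and treat a PPA above 90% under it as settling the matter. That reasoning covers indeterminate ASIS and equivocal results. It has no support for attempted failures, because no formula counts them.

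The results are meant to support FDA clearance, so the handling should be stated once and its effect shown.

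**Working it through.** **1. Follow one failed test through the plan.** Take an infected site where the test under consideration is invalid and its repeat is invalid.
- Protocol 2.3: final result NR, for the ASIS determination and for the analyses.
- Tables 4/5 and 11/13: row excluded.
- Primary PPA, A/(A+B+C+F) or A/(A+B+D): no term for it.
- Sensitivity formulas in SAP Tables 12 and 14: none has a term for it. The missing-data analysis reassigns only cells B, D, E, F and H (Table 12) or C and D (Table 14).

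If the first result had been equivocal (Company 2, or Company 3 for CT), the test would sit in cell B or H and count against the assay at an infected or not-infected site.

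**2. Reproduce the design figures (protocol 6.3).** Inputs: goal 90%, true PPA 96%, two-sided alpha 0.05.

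n = [(1.96·√(0.90·0.10) + z_power·√(0.96·0.04)) / 0.06]² = 157.5, 173.8 and 195.6 for 80%, 85% and 90% power. The plan states 157, 174 and 196.

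**3. Failures needed to cross 90%.** Score lower bound, with z = 1.96:

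L = [p + z²/2n − z·√(p(1−p)/n + z²/4n²)] / (1 + z²/n)

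Failures are added to the denominator on top of the resolved infected sites.

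| Resolved result | L, failures excluded | Failures that cross 90% | Counted | L, counted |
|---|---|---|---|---|
| 151/157 (96.2%) | 91.9% | 3 | 151/160 | 89.7% |
| 167/174 (96.0%) | 91.9% | 3 | 167/177 | 89.9% |
| 188/196 (95.9%) | 92.2% | 4 | 188/200 | 89.8% |
| 154/157 (98.1%) | 94.5% | 6 | 154/163 | 89.8% |
| 171/174 (98.3%) | 95.0% | 8 | 171/182 | 89.5% |
| 192/196 (98.0%) | 94.9% | 9 | 192/205 | 89.5% |

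Example, 188/200: (0.9400 + 0.0096 − 0.0343)/1.0192 = 0.898. In the first three rows the failures are 3/160 = 1.9%, 3/177 = 1.7% and 4/200 = 2.0% of infected sites.

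**4. How often the two treatments would disagree.** The failure rate u is an assumption; the documents give none. With 196 infected sites including failures, failures ~ Bin(196, u) and positives ~ Bin(196 − failures, PPA). The table gives the probability that the bound exceeds 90% with failures excluded but not with failures counted.

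| True PPA among resolved tests | u = 0.1% | 0.5% | 1% | 2% |
|---|---|---|---|---|
| 96% | 1.4% | 8% | 17% | 39% |
| 97% | 0.4% | 2.8% | 7.7% | 24% |
| 98% | 0.03% | 0.3% | 1.5% | 9% |

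If failures instead come on top of 196 resolved sites, the 96% row becomes 8%, 18% and 42% at u = 0.5%, 1% and 2%.

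**5. NPA.** Assume 2,775 not-infected sites (3,000 × 0.925) and NPA 99% among resolved tests. With no failures, 2,747/2,775 has a lower bound of 98.5%. With 5% failing, 2,610/2,775 has a lower bound of 93.1%.

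**The case against.** **The plan has a workable rule.** The protocol codes double failures as NR for the analyses and excludes the NR row without condition. The sentence about tests never attempted does not say *only*, and no passage puts attempted failures in a denominator. This stands. A reader might infer that the documents prescribe two competing primary results. They do not: the formulas as written drop these failures. What remains is that the stated reasons do not cover what the row does.

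**Failures are not hidden.** SAP Table 8 tabulates invalid results for Companies 1 and 2, and error and no result separately for Company 1. Re-test frequencies and results are planned by platform, site and organism. SAP 5.4.3 plans a "Cross comparison of number (%) of results of test under consideration versus ASIS", and SAP 5.4.2 says the outcomes evaluated will include no result or invalid. This also stands, so it would be wrong to say the plan conceals failures. But these are counts, the cross-table merges no result with invalid, and the SAP 5.4.2 sentence comes with no formula. None of them yields a PPA or NPA that includes failures.

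**Not every failed repeat is affected.** A reader might take the point to cover any test whose repeat fails. It does not, because results that began as equivocal stay equivocal.

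**The size rests on an assumed rate.** For double failures, u is the rate of failing on both runs. If runs failed independently (itself an assumption), 0.5%, 1% and 2% would need initial failure rates of about 7%, 10% and 14% (square roots). The larger probabilities also use the design's 96%, which is close to the goal. Both remarks are fair.

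**Counting failures as non-agreement is one choice among several.** Agreement among valid results, with failure rates reported beside it, is another. That is why the counted version is proposed as a sensitivity analysis and not as the primary one.

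**Conclusion.** The point holds for a defined group: tests under consideration whose first result was invalid, error or (Company 1) no result, and whose repeat failed the same way or is missing. They drop out of every PPA and NPA formula, the text and SAP footnotes do not give a reason that covers them, and NR is defined in two ways. The description of the primary definition as the most conservative is unsupported with respect to this group.

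The practical size is unknown, and it is zero if no such failures occur. At an observed PPA near 96%, 3 or 4 among the infected sites are enough to move the lower bound below 90%; near 98% it takes 6 to 9. These tipping points rest on the Score bound, the planned 157 to 196 infected sites and failures counted as non-agreement. The probabilities of disagreement rest in addition on assumed failure rates. NPA conclusions are safe under the assumptions shown. A reader might infer that a PPA conclusion is likely to be overturned; without a failure rate the documents do not support that. The change should be made because it is cheap and removes the doubt.

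**What to change.** 1. Use one NR definition in both documents, matching the note to protocol Table 2, and correct both abbreviation lists.
2. Split the No result row of protocol Tables 4 and 5 and SAP Tables 11 and 13 into *never tested* and *attempted, final NR*. The second is an initial invalid, error or no result with a failed or missing repeat, and leaves out anything coded equivocal. Make the text and footnotes state the same primary rule as the row.
3. Add one sensitivity analysis to SAP Tables 12 and 14, for all three assays, counting *attempted, final NR* as non-agreement. Let J and K be those at infected and not-infected sites:
   - Table 12: PPA = A/(A+B+C+F+J); NPA = I/(G+H+I+D+K)
   - Table 14: PPA = A/(A+B+D+J); NPA = F/(C+E+F+K)

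   Attempted failures at indeterminate sites stay out of both, as cell E does in the primary analysis.
4. Limit the statement that the primary definition is the most conservative to the handling of indeterminate and equivocal results.

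Cost: wording, one split row and one extra analysis on laboratory data already held. The sensitivity estimates will be slightly less favourable if failures occurred.

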6.3 Sample Size

For each assay, PPA and NPA³⁵ will be estimated for each of three diagnostic tests defined by pathogen - anatomical site combinations:

- *Neisseria gonorrhoeae* in the rectum
- *Neisseria gonorrhoeae* in the pharynx
- *Chlamydia trachomatis* in the rectum
- *Chlamydia trachomatis* in the pharynx

Each pathogen/anatomic site combination will be evaluated by constructing 95% Score confidence interval estimates for PPA and NPA and evaluating whether 90% can be ruled out by the lower bound of the CI with reasonable confidence.

NPA is expected to be greater than PPA and there will be considerably more not-infected than infected anatomic site, implying that there will be greater power for evaluating NPA. Thus it will suffice to size the study to evaluate PPA.

Assuming that the true PPA is 96%,¹³ then 157, 174, and 196 evaluable participants that are infected are needed to have 80%, 85%, and 90% power respectively to demonstrate a PPA of greater than 90%. Since all of the participants will contribute to the evaluation of all three pathogen-anatomical site diagnostic tests, it will suffice to size the study for the diagnostic test with the lowest expected prevalence (except CT in the pharynx). The study will be more than sufficiently sized for more prevalent disease.

It is expected that the disease prevalence of NG in the rectum, NG in the pharynx, and CT in the rectum will each be greater than 7.5% in the population under evaluation.^{13,14,16-20} Table 3 summarizes the required number of participants to have 80% and 90% probabilities of obtaining the 157, 174, and 196 evaluable participants that are disease-positive to have 80%, 85%, and 90% power when the true prevalence of disease is 7.5%, 10%, and 12.5%.

Table 3: Sample size required number to have 80% and 90% probabilities of obtaining the 157, 174, and 196 evaluable participants that are disease-positive when the true prevalence of disease is 7.5%, 10%, and 12.5% in order to have 80%, 85%, and 90% power (two-sided alpha=0.05) to conclude that sensitivity is greater than 90% when the true sensitivity is 96%.

| Prevalence of Disease Positive | Power | Required Disease Positive to Obtain Power | Required Sample Size to have 80% probability of obtaining required Disease positive participants | Required Sample Size to have 90% probability of obtaining required Disease positive participants |
|--------------------------------|-------|---|--|--|
| 7.5% | 80% | 157 | 2250 | 2325 |

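### For assays that can read equivocal, the primary PPA and NPA leave out one indeterminate cell, so the primary analysis is not always the most conservative one

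*Protocol*

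**What the plan says.** Protocol 6.6.1 states the principle: "Indeterminate ASIS results will be counted against the results for the test under consideration, as described in Tables 4 and 5". Table 4 covers the assays with an equivocal category, which are Company 2 for both organisms and Company 3 for CT. Its primary formulas are PPA = A/(A+B+C+F) and NPA = I/(G+H+I+D), and SAP Table 12 repeats them. By ASIS (infected, indeterminate, not infected), the cells are A, D, G for a positive test, B, E, H for an equivocal test and C, F, I for a negative test. Only the no-result row is marked for exclusion.

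Of this approach the protocol says "The primary definition is the most conservative but is biased downwards". SAP 5.4.2 makes the same claim and adds "If PPA is >90% under this scenario, then the conclusion of PPA >90% is clear". The performance target in Protocol 6.3 is "evaluating whether 90% can be ruled out by the lower bound of the CI with reasonable confidence".

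An equivocal reading can be final. For Company 2, Protocol 2.3 says "If the repeat test result returns equivocal, the final test result will be considered an equivocal test result for the ASIS determination", and there is a like rule for Company 3 CT. SAP 5.1 also keeps an equivocal result when the expected repeat is missing.

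**The concern.** In the primary formulas, a negative test on an indeterminate site (F) counts against PPA and a positive test on one (D) counts against NPA. Equivocal tests on sites of known status also count against the test: B in PPA, H in NPA. Cell E is the only cell of the nine that enters neither primary formula, although it is both an indeterminate ASIS result and a non-correct reading. No reason is given.

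Two sensitivity analyses in the same tables do count E: PPA with all indeterminates infected, and NPA with all indeterminates not infected. Either can therefore be lower than the primary analysis that is described as the most conservative. At stake is the inference to PPA above 90%. A primary lower bound above 90% could stand beside a planned sensitivity analysis whose lower bound is below 90%, while the text tells the reader that the primary settles the question.

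**Working it through.** **Inputs.** From Protocol 6.3: 95% Score interval (two-sided alpha 0.05), threshold 90%, assumed true PPA 96%, and 157, 174 and 196 infected participants for 80%, 85% and 90% power. Formulas are from Protocol Table 4 and its sensitivity list, and SAP Table 12. The count in E is not given; the range 0 to 5 is an assumption.

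**Step 1: the plan's own figure.** One-sample score test, n = [(1.96·√(0.90·0.10) + z_power·√(0.96·0.04)) / 0.06]². This gives 157.5, 173.8 and 195.6, which reproduces the stated 157, 174 and 196.

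**Step 2: when the primary is not the lowest.** Let M = A+B+C+F. The all-infected PPA is below the primary when (A+D)/(M+D+E) < A/M. Cross-multiplying gives D(M−A) < A·E, that is D(B+C+F) < A·E. With E=0 this cannot happen. With E>0 and D=0 it always happens (for A>0). Likewise, the all-not-infected NPA is below the primary NPA when F(D+G+H) < I·E.

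Enumeration agrees (A = 10 to 190 in tens, B and C 0 to 2, D and F 0 to 3). With E=0, no listed all-infected or all-not-infected PPA fell below the primary in 2,736 tables. With E = 1 to 3, one did in 8,178 of 8,208. The Table 5 formulas, which have no equivocal row, gave no violations.

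**Step 3: effect on the 90% decision.** Score lower bounds with E added to the denominator (the same as the all-infected result when D=0):

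| Primary A/M | Lower bound | Smallest E that fails | Lower bound with E |
|---|---|---|---|
| 149/157 | 90.27% | 1 (149/158) | 89.53% |
| 151/157 | 91.91% | 3 (151/160) | 89.66% |
| 165/174 | 90.46% | 1 (165/175) | 89.80% |
| 167/174 | 91.93% | 3 (167/177) | 89.91% |
| 185/196 | 90.23% | 1 (185/197) | 89.66% |
| 188/196 | 92.15% | 4 (188/200) | 89.81% |

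The first row for each M is the smallest A that passes; the second is about 96% of M.

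**Step 4: D can offset E.** Take A=188, B=2, C=6, F=2, so M=198 and the primary bound is 90.95%. With E=1 and D=0 the all-infected bound is 90.37%, still a pass. With E=2 it fails for D = 0 to 3 (89.81% to 89.95%), passes by a hair at D=4 (192/204, 90.001%) and passes at D=5 (90.05%).

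**Step 5: chance of passing.** Take A as Binomial(M, 0.96), E fixed and D=0. The chance of a lower bound above 90% for E = 0, 1, 2, 3 is 82%, 71%, 56%, 40% at M=157 and 90%, 84%, 74%, 61% at M=196. These are conditional on E, not forecasts.

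**Step 6: NPA.** With an assumed 2600/2640, NPA is 98.48% (bound 97.94%). At E=5 it is 2600/2645 = 98.30% (bound 97.73%). No decision changes.

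**The case against.** E is a narrow cell. It needs a final equivocal reading, after a repeat where one is obtained, on a site whose ASIS is also indeterminate. For Company 2 NG, neither comparator has an equivocal category, which closes some routes. Suppose, as an assumption, that the two events are independent and 2,833 participants are analysed (3,000 maximum less the 167 excluded). Rates of 0.5% each then give an expected E of 2,833×0.005×0.005 = 0.07, and 1% each gives 0.28, about a 25% chance of at least one. Averaged over a Poisson E with those means, the E-inclusive chance of passing at M=157 is about 81% and 79%, against 82% at E=0. The fixed-E probabilities above should not be read as the expected loss. Positive correlation, as with low-load samples, would raise E, but the documents give no rate for either event.

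The plan also says its primary analysis follows FDA guidance. The SAP revision list shows the Table 12 formulas were revisited and F and D were added. The guidance may leave E out; that cannot be checked here. Finally, the cross-tables show E, the all-infected and all-not-infected analyses include it, and the plot in SAP 5.4.3(h) varies the share of indeterminates taken as positive, so a reversal would be visible.

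All of this bears on how often the gap matters and on which remedy to choose. None of it makes the two statements true: guidance may fix a formula, but not whether that formula is the worst case. Visibility helps less than it seems, because the text directs the reader to the primary and warns that the alternatives may not be conservative.

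**Conclusion.** The concern holds. For Company 2 and for Company 3 CT, the claim that the primary is the most conservative analysis, and that a PPA above 90% under it is clear, is guaranteed only when E=0. The algebra needs no assumption.

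The practical size depends on E and D, which the documents do not give. The 90% decision turns on one such specimen at the smallest passing result, and on three or four when the observed PPA is near 96%, taking D=0; larger D weakens the effect in the all-infected analysis. Results far above the threshold are safe, NPA conclusions do not change in practice, and Company 1 and Company 3 NG are unaffected. It should be fixed before the analysis, because a worst-case argument should not rest on an unstated assumption that one cell is empty.

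**What to change.** In Protocol Table 4 and SAP Table 12, set the primary to PPA = A/(A+B+C+E+F) and NPA = I/(D+E+G+H+I), and say that each is a separate worst case, so that an E specimen counts in both denominators.

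This makes the claim true for every assignment of indeterminate sites to infected or not infected, including one by symptom status. If d ≤ D, e ≤ E and f ≤ F of them are called infected, then (A+d)/(A+B+C+d+e+f) ≥ A/(A+B+C+e+f) ≥ A/(A+B+C+E+F). The same argument applies to NPA.

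If the cited guidance requires E to be left out, keep the formulas. In that case, withdraw the most-conservative and clear-conclusion statements for these assays in Protocol 6.6.1 and SAP 5.4.2, and report the E-inclusive PPA and NPA with Score intervals beside the primary.

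The cost is one formula change, or two sentences and one table row, in each document. No new data are needed. If E>0, the first option lowers the primary estimates for Company 2 and Company 3 CT, and a result close to the threshold could then fail.
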